Study Population:	
Approximately 70 subjects is needed to assess the primary outcome, measured as the percentage of repairs that heal and remain intact after 1 year.
 
All statistical comparisons will be made using the Statistical Package for Social Science (SPSS) version 16.0 software.
 
Inclusion Criteria:
 
 1. Patients with a large (2.5-5 cm) to massive (>5 cm) rotator cuff tear who will be undergoing open or arthroscopic repair. The cuff tear size will be determined on either pre-operative magnetic resonance imaging (MRI), or ultrasound (US), or intra-operative measurements, or computerized tomography (CT). 2. Patients who are willing and able to provide written informed consent for their involvement in the study. 3. Patients who meet criteria for RCR surgery. 4. Patients older than 18 years of age. 
Exclusion criteria:
 
 1. Those with a known sensitivity to materials of porcine origin. 2. Patients with addiction to illegal drugs, solvents or alcohol who are actively using or have previously attempted and failed a treatment program. 3. Patients with bacteremia, a systemic infection, or infection of the surgical site. 4. All those who are prisoners. 5. Patients who are pregnant or nursing. 6. All those with a condition that may limit a patient's ability to finalize the study or that may cause an undue risk to the patient's health and well-being.
Description of Site/Facilities Enrolling Participants:	
Levitetz Department of Orthopedic Surgery Department of Anesthesiology
 
Locations:
 
Cleveland Clinic Florida – Weston [name]
 
Cleveland Clinic Florida – Coral Springs [name]

Study Duration:	Subjects will be followed for 1 year.
Data Collection:	Electronic (REDCap and EPIC) database (please see Data Handling and Record Keeping).

Statistical Reporting:	Statistical analysis will be performed by a biostatistician at Cleveland Clinic.
-------------------------------	--

Schedule of Activities (SoA)

	Visit 1	Visit 2	Visit 3	Visit 4	Visit 6	Visit 5
Assessment	Screening (Pre-Op)	6 weeks Post-op	3 mo. Post-op	6 mo. Post-op	9 mo. Post-op	1 year Post-op
Eligibility	X					
Informed Consent	X					
Medical History and Physical Exam	X					
MRI						X
US		X	X	X	X	X
Shoulder Outcome Surveys	X	X	X	X	X	X

Time and Events Schedule: Summary Table

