Eligible patients will be evaluated according to the pre-, intra- and post- operative assessment plans, delineated below, as well as the time and events schedule. All clinical results will be assessed during the period of hospital stay.

A. Preoperative Assessments

The following assessments/tests will be taken prior to patient operative treatment.

- Eligibility criteria, including informed consent.
- Age, gender, height, weight, BMI
- Primary diagnosis
- Medical History
- Physical Exam
- Current medications
- American Society of Anesthesiologists (ASA) risk
- Smoking status
- Imaging of shoulder
- Shoulder outcome surveys (SSV, ASES, Constant, VR12, WORC)

B. Operative Assessments

The following medical information will be collected from the Operative and Anesthesia records.

- Tear size, retraction, quality of tissue
- Length of surgery
- Possible intraoperative arthroscopic photographs

- Implants used
- Quality of repair

C. Postoperative Assessments

The following information will be collected after surgery: standard clinical follow-up PE and history, medications and serial US exams at 6 weeks, 3 months, 6 months, 9 months and 1 year postop, and MRI exam at 1 year postop. All US examinations will be performed by one Board Certified and Fellowship trained Sports Medicine physician in the office and coordinated with scheduled follow-up appointments. Shoulder outcome forms will also be collected at each follow up visit (listed below):

4. Data Collection and Analysis

The primary clinical outcomes to be measured and subsequently evaluated will be the following:

- d. Success as defined by tendon healing after rotator cuff repair, as indicated based on MRI at 1 year.
- e. Comparison of tendon healing will be assessed using US imaging modalities versus MRI at 1 year time point.
- f. Progress of tendon healing based on US will be used as predictive data for 1 year success (based on primary outcome).

The secondary clinical outcomes to be measured and subsequently evaluated will be the patient satisfaction, quality of life, and shoulder function, to be determined with the following outcome measures:

- g. The Veterans Rand 12-item Health Survey (VR-12).
- h. The American Shoulder and Elbow Surgeons Shoulder (ASES)
- i. The Western Ontario Rotator Cuff Index (WORC).
- j. Shoulder activity level as per Brophy et al. [15].
- k. Subjective Shoulder Value (SSV)
- l. Constant Shoulder Score (Constant)

5. Sample Size Justification and Statistical Analysis

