Approximately 70 subjects are needed to assess the primary outcome, measured as the percentage of repairs that heal and remain intact after 1 year. A re-tear rate of 40% is expected in patients who have undergone rotator cuff repair for large and massive rotator cuff tears, based on the current literature (reference ted below). We anticipate that in this study, the percentage of re-tears in the augmented group will be reduced by

approximately half (~20%), while the control group would experience rates of re-tear comparable to what is reported in the current literature (~40%). Reducing this rate by half would be clinically meaningful. An SD of 15% within groups was allowed. Power analysis indicated that 20 patients in each group would provide sufficient power to identify statistical significance in healing rates between the control and augmented groups. With the assumption that the control group will have a failure rate of approximately 40% and the augmented group will have a failure rate of approximately 20%, at least 34 should be randomized in the control group and 26 in the augmented group. It is estimated that an overall fewer percentage of subjects initially randomized to the control group will complete the trial as augmentation may be required due to tear severity and other procedure variables. Those patients randomized to the control arm and withdrawn for repair by augmentation may be followed for safety.

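### The primary sample-size calculation gives a yes/no outcome an SD of 15%; 20 per group has about 19–29% power, and 35 per arm with no losses only about 36–45%

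*Combined protocol and SAP*

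**What the plan says.** The primary outcome in Section 4 is "Success as defined by tendon healing after rotator cuff repair, as indicated based on MRI at 1 year". Section 5 treats it as a proportion, "measured as the percentage of repairs that heal and remain intact after 1 year".

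Section 5 then gives these inputs and conclusions:

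- Control rate: "A re-tear rate of 40% is expected in patients who have undergone rotator cuff repair for large and massive rotator cuff tears". The augmented group is expected to have about half that, roughly 20%.
- Variability: "An SD of 15% within groups was allowed".
- Conclusion: "20 patients in each group would provide sufficient power to identify statistical significance in healing rates between the control and augmented groups". No numerical power is given for this outcome, and no test or formula is named.
- Numbers to randomise: at least 34 control and 26 augmented.
- Total: "Approximately 70 subjects are needed to assess the primary outcome, measured as the percentage of repairs that heal and remain intact after 1 year". The synopsis (Study Population) repeats this, and Section 1 randomises 35 to each arm.
- Significance: two-sided p below 0.05.

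The only numerical power target in the plan is 0.8, in the separate calculation for the ASES score, a secondary outcome. The summary of changes attributes the increase to 70 to high drop-out.

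**The concern.** Each patient contributes a yes or a no. For such an outcome the SD is not a separate assumption: once the rate is set, it is sqrt(p(1−p)). An SD of 15% would be far too small for individual yes/no results at rates of 20% to 40%. A within-group SD belongs to a comparison of means, and it makes a 20-point difference look very easy to detect.

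The plan therefore claims a property that the design lacks. If the graft works exactly as hoped, an effect that Section 5 itself regards as clinically meaningful, the most likely result is still a non-significant one. Anyone relying on the claim of adequate power would misread that result as a finding against the graft.

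**Working it through.** **Inputs (Sections 1 and 5).** Re-tear 0.40 against 0.20; SD 0.15; alpha 0.05 two-sided; 20 per group claimed; 34 and 26 as minimum numbers to randomise; 35 per arm planned. The 80% benchmark is the conventional one and is the figure the plan uses for ASES.

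**1. Can the plan's 20 per group be reproduced?**

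Taking the SD at face value, as a comparison of means: d = 0.20/0.15 = 1.33.

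- n per group = 2(1.960 + 0.842)²/1.33² = 8.8, so 9 by the normal approximation. With the t distribution, 10 per group gives 80.5% power.
- For 90% power the normal approximation gives 12.
- At 20 per group, t-test power is 98.4%.

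So 20 looks ample on this reading, but it is not the answer at 80% or 90% power. Only a target near 99% (21 per group) comes close, and no such target is stated.

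**2. The SD of the actual outcome**

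- Control: sqrt(0.40 × 0.60) = 0.490
- Augmented: sqrt(0.20 × 0.80) = 0.400

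These are roughly three times the 0.15 used.

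**3. Sample size for two proportions**

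With mean rate 0.30:

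n = [1.960 × sqrt(2 × 0.30 × 0.70) + 0.842 × sqrt(0.24 + 0.16)]² / 0.20²
= (1.270 + 0.532)² / 0.04 = 81.2

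That is 82 per arm for 80% power, or 91 with continuity correction. For 90% power it is 109 (119 corrected).

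**4. Power at the plan's numbers**

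The normal approximation at 35 per arm is Φ[(0.20 − 1.960 × sqrt(0.42/35)) / sqrt(0.40/35)] = Φ[(0.200 − 0.2147)/0.1069] = Φ(−0.138) = 44.5%. At 20 per arm it is 27.6%. Summing exact binomial probabilities over all possible results gives:

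| Evaluable patients | Chi-square | Fisher |
|---|---|---|
| 20 per group (the claim) | 29.1% | 19.2% |
| 28 per arm (35 less an assumed 20% loss) | 38.2% | 28.2% |
| 34 control, 26 augmented | 37.5% | 33.0% |
| 35 per arm, no loss | 45.3% | 35.7% |
| 82 per arm | 80.7% | 75.9% |

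A one-sided test, which the plan does not use, would reach only 39% at 20 per group and 57% at 35 (normal approximation).

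**5. What 35 per arm can detect**

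Holding control at 40% with all 35 per arm evaluable, chi-square power is 82% for an augmented rate of 11% and 78% for 12%, so 80% power needs about 11%. With Fisher's test it needs about 9.6%.

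**6. Precision**

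Expected 95% CI half-width for the difference at 35 per arm: 1.96 × sqrt(0.24/35 + 0.16/35) = 0.210, or 21 points against an effect sought of 20.

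**The case against.** The arithmetic is not in dispute. The fair objections concern how far it reaches.

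- *The plan names no formula, so the use of a continuous method is inferred.* True. The inference is strong, because the SD is the only stated input that makes 20 per group adequate. The conclusion does not depend on it: 20 per group is inadequate for the stated rates however it was obtained.
- *No power figure is stated for the primary outcome.* Also true, and 80% is borrowed from convention and from the ASES calculation. But the plan does assert that power is sufficient, and 19–29% would not ordinarily be called that.
- *The 20 counts completers; 34 and 26, then 70 in total, are enrolment figures that allow for losses.* This works against the plan. The 36–45% at 35 per arm is a best case with everyone evaluable, yet Section 5 expects control patients to be withdrawn and the summary of changes cites heavy drop-out.
- *Section 5 re-checks power once 15 per group have data.* That check is post hoc and has no decision rule, so it cannot supply power missing from the start.
- *Leading with a confidence interval is a preference.* In part. The necessary correction is to remove or replace the unsupported power claim. The interval is the sensible way to report a trial of this size.

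**Conclusion.** The concern holds. An SD of 15% is incompatible with the yes/no primary outcome, and 20 per group does not follow from the stated inputs at 80% or 90% power by either method. For 40% against 20% at two-sided 0.05, 20 per group is about a quarter of the 82 needed for 80% power. The planned 70 patients leave power below one half even with complete follow-up.

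These figures rest on the plan's own rates and significance level and on independent patients. The ranges reflect the choice between chi-square and Fisher, since the plan names no test. The 20% loss behind the 28-per-arm row is an assumption. This must be corrected, because the plan states something about the design that is not so.

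**What to change.** In Section 5, and in the synopsis where it repeats the claim:

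1. Delete the sentence on the SD and the statement that 20 per group is sufficient. Delete also the minimum of 34 and 26, which is built on the 20: 20/0.6 = 33.3, rounded up to 34, and 20/0.8 = 25, close to the stated 26.
2. Reword the claim that about 70 subjects are needed for the primary outcome, since no power calculation then supports it. Give 70 as the planned enrolment.
3. Insert a two-proportion calculation: before losses, 35 per arm gives about 45% power (chi-square) or 36% (Fisher) for 40% against 20%. Name the test to be used.
4. State the detectable difference with its conditions: before losses, 80% power requires an augmented rate of about 11% by chi-square, or about 9.6% by Fisher, against 40% in control.
5. State that the primary result is the between-arm difference in healing with its 95% confidence interval (expected half-width about 21 points at 35 per arm), and that a non-significant result will not be read as absence of benefit.

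No extra patients and no change to procedures are requested. The cost is a rewording of Section 5 and the synopsis, and an openly less favourable account of the trial's power.

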A power analysis was also considered for shoulder function, a secondary clinical outcome. It demonstrated that at least thirty-four cases must complete the study (seventeen cases in each arm- augmented and control) in order to assess the difference between each group. This sample size was statistically derived by an ASES score power analysis, using a power of 0.8, an effect size d of 0.9, an alpha error probability of 0.05, and an allocation ratio of 1. This is assuming an ASES score of 84 at 12 months postsurgical repair in the augmented group (standard deviation of 16) and 72 (standard deviation of 12) for the control group. The ASES data used was derived from a recently completed ArthroFlex rotator cuff repair study for which data is on file at LifeNet Health. Again, with the assumption that the control group will have a failure rate of approximately 40% and the augmented group will have a failure rate of approximately 20%, at least 30 should be randomized in the control group and 22 in the augmented group to assess a difference in shoulder function.

Once data is acquired for 15 subjects in each group, a post-hoc power analysis will be conducted to confirm that alpha and beta error probabilities are still under the accepted limits.

The primary analysis will be conducted on both the intent to treat and the per protocol populations. The intent to treat population will be comprised of all subjects that have completed rotator cuff repair surgery. The per protocol population will be comprised of all subjects that have completed all study visits and did not have any major protocol violations (e.g., missed visits, noncompliance with postsurgical instructions, etc.). Standard adjustments to analyses for pre-specified or baseline-suggested clinical covariates will be made; these covariate-adjusted analyses will be considered secondary analyses. Primary analysis results will be declared statistically significant if the two-sided p-value is less than 0.05.

Safety analyses will be performed on the intent to treat population and will include the incidence of treatment-emergent AEs and clinically significant changes in vital signs and

physical examinations. Impact of treatment on infection rate, treatment emergent AEs, and changes in vital signs and physical examination will all be assessed.

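### The randomisation targets of 34/26 and 30/22 appear to treat expected re-tears as patient losses, and the plan gives no separate non-completion rate

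*Combined protocol and SAP*

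**What the plan says.** Section 5 expects re-tears in about 40% of controls and about 20% of augmented patients. It continues: "Power analysis indicated that 20 patients in each group would provide sufficient power". Then, assuming a failure rate of about 40% and 20%, it concludes that "at least 34 should be randomized in the control group and 26 in the augmented group". The next sentence turns to completion: "It is estimated that an overall fewer percentage of subjects initially randomized to the control group will complete the trial", because some controls may need augmentation. Of these it says: "Those patients randomized to the control arm and withdrawn for repair by augmentation may be followed for safety".

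For ASES, the same section says that "at least thirty-four cases must complete the study", 17 in each arm. It repeats the 40%/20% assumption and asks that "at least 30 should be randomized in the control group and 22 in the augmented group to assess a difference in shoulder function".

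The primary outcome is tendon healing on the 1-year MRI (Section 4). On the analysis set, Section 5 says: "The intent to treat population will be comprised of all subjects that have completed rotator cuff repair surgery". Section 1 now plans 70 patients, 35 per arm. The Summary of Changes attributes the increase to drop-out but gives no rate.

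**The concern.** The rates used to inflate the sample equal the rates assumed for the primary outcome. A patient whose repair has re-torn at 1 year has had surgery, belongs to the intent-to-treat population as defined, supplies a primary outcome of not healed, and can still complete an ASES form. Inflating for such patients treats outcome events as missing data.

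Failure rate might instead mean failure to complete. The 40% and 20% then have no numerical source. The one reason offered, controls needing augmentation, cannot explain a 20% loss in the augmented arm.

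On either reading the real loss is unquantified: missed MRIs, drop-out, and controls withdrawn for augmentation. A reader cannot tell how many evaluable patients 70 randomised patients should yield, or what power follows.

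**Working it through.** **Inputs.** From Section 5: 20 per group (healing), 17 per arm (ASES), rates of 40% and 20%, two-sided 0.05 for the primary analysis, ASES means 84 and 72 with SDs 16 and 12. From Section 1: 35 per arm.

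**Step 1: reproduce the targets.** The plan shows no formula. The usual inflation is n/(1 − d).

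| Target | n/(1 − d) | Rounded up | Rounded up to even | Stated |
|---|---|---|---|---|
| Healing, control | 20/0.6 = 33.3 | 34 | 34 | 34 |
| Healing, augmented | 20/0.8 = 25.0 | 25 | 26 | 26 |
| ASES, control | 17/0.6 = 28.3 | 29 | 30 | 30 |
| ASES, augmented | 17/0.8 = 21.25 | 22 | 22 | 22 |

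Plain rounding up is within one patient of every target. Rounding up to even numbers matches all four, though the plan states no such rule. The alternative n(1 + d) gives 28/24 and 24/21 and misses both control targets by six.

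**Step 2: evaluable patients implied by 35:35.** If failure means re-tear, the allowance contains no true loss, so 70 is only an upper bound. If it means non-completion, 35 × 0.6 = 21 controls and 35 × 0.8 = 28 augmented patients remain, 49 in total.

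**Step 3: power.** The plan names no test for healing. I used the pooled normal approximation for 40% v 20%:

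power = Φ[(0.20 − 1.96·SE₀)/SE₁]

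SE₀ uses the pooled proportion and SE₁ the separate proportions.

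- 35 v 35: SE₀ = √(0.3 × 0.7 × 2/35) = 0.1095; SE₁ = √((0.24 + 0.16)/35) = 0.1069; power = Φ(−0.14) = 0.445.
- 21 v 28: pooled proportion 14/49 = 0.286; SE₀ = 0.1304; SE₁ = √(0.24/21 + 0.16/28) = 0.1309; power = Φ(−0.42) = 0.336.

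For ASES I used a two-sided t-test at 0.05 with d = 12/√((256 + 144)/2) = 0.849, from the stated means and SDs (the plan quotes 0.9).

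| Evaluable (control v augmented) | Basis | Primary power | ASES power |
|---|---|---|---|
| 35 v 35 | no loss | 0.445 | 0.938 |
| 31 v 31 | assumed 10% loss | 0.402 | 0.908 |
| 28 v 28 | assumed 20% loss | 0.369 | 0.877 |
| 24 v 24 | assumed 30% loss | 0.323 | 0.821 |
| 21 v 28 | 40%/20% as non-completion | 0.336 | 0.821 |

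The equal losses of 10% to 30% are my assumptions, with evaluable numbers rounded down.

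**Step 4: would a conventional loss allowance need more patients?** On the plan's own bases, equal loss of 10%, 20% or 30% calls for 23, 25 or 29 per arm (healing) and 19, 22 or 25 per arm (ASES). The control targets are therefore not too small on those bases, and 35 per arm covers all of these figures.

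**Step 5: withdrawn controls.** Suppose, as an assumption, that 20% of controls are augmented. Excluding them leaves 28 v 35 and primary power of 0.413. Keeping them, with a re-tear rate of 20%, gives a control rate of 0.8 × 0.40 + 0.2 × 0.20 = 0.36 and power of 0.317 at 35 v 35. What counts as a loss cannot be settled until their handling is.

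**The case against.** The strongest reply is that failure rate means failure to complete. The next sentence is about completion and gives a reason for greater loss among controls, and the ASES inflation starts from patients who must complete. The formula is also inferred: plain rounding misses two of the four targets by one, and the even-number rule was fitted afterwards. These points stand, and they are why I say the targets appear to rest on re-tear rates. They do not rescue the justification. Under this reading the plan gives a direction for the control arm, but no source for either percentage and no reason for 20% in the augmented arm.

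A second reply is that nothing operational changes: 35:35 exceeds every target, and deleting the targets alters no power. That is correct. The defect lies in the justification and in the undisclosed attrition.

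A third is that the primary powers depend on the test. They do: at 35:35, Fisher's exact test gives about 36% instead of 45%. The low level mainly reflects the base of 20, which itself gives only about 28% power at 20 per arm, and that is a separate matter.

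Finally, deleting the targets might seem to presume the re-tear reading. It does not. An observed drop-out rate is a better basis than 40%/20% whichever was meant.

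**Conclusion.** The concern holds. The four targets are within one patient of what results from using the 40% and 20% re-tear rates as loss rates, and the documents contain no separate non-completion figure. The allowance is invalid if failure means re-tear and unsupported if it means non-completion. The plan therefore leaves the expected number of 1-year MRIs undefined, between 49 and an upper bound of 70 on its own figures. Across that range primary power runs from about 34% to 45% and ASES power from about 82% to 94%, given the plan's effect assumptions and the tests named above. Enrolment is not put at risk by this point. It should be corrected because the section's sample-size and power statements rest on it.

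**What to change.** In Section 5:

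1. Delete the 34/26 and 30/22 targets and the failure-rate inflation.
2. State that a re-tear is an observed not-healed outcome and not a loss. The 1-year MRI endpoint stays as it is.
3. State an expected loss to the 1-year MRI, taken from drop-out to date pooled over both arms, and restate evaluable patients per arm and power from 35:35.
4. Before counting any group as lost, reconcile three statements: Section 5 on controls withdrawn for augmentation and possibly followed for safety; Section 2.D.3 on irreparable tears, which stay in the study but are analysed separately; and the intent-to-treat definition in Section 5. Patients kept in that population with a 1-year MRI are not losses.
5. Make this change together with the correction of the base of 20, so that the claim of sufficient power is rewritten once.

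The cost is a rewording of Section 5, a pooled count from the study database, and a less favourable stated primary power. No patients are added and the endpoint is unchanged.

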Safety data will be summarized with descriptive statistics by treatment group and also by visit, where applicable. AE data will be listed individually and summarized by system organ class and preferred terms within a system organ class for each treatment group.

All statistical comparisons will be made using the Statistical Package for Social Science (SPSS) version 16.0 software. Results will be reported as an aggregate.

Statistical analysis will be performed by the orthopaedic research fellows in conjunction with Cleveland Clinic-Main biostatistician.

6. Study Product Description

ArthroFlex (A-FLEX) is not considered investigational and is currently available. The material is classified as a human and cellular tissue product under Food and Drug Administration (FDA) regulations and thus is not subject to any clinical evaluations before use. LifeNet Health uses several steps to ensure that allograft tissue is safe for use with patients. Extensive donor screening is performed to prevent risk of disease transmissions. There is a medical and social history taken from every donor, and questionable donors are refused. Blood is drawn from each donor for testing to rule out diseases such as HIV, hepatitis, and syphilis. Each section of recovered tissue is tested for any bacteria. In addition, tissue used to make A-FLEX is treated with antibiotic to inactivate bacteria. The tissue is also cleaned thoroughly with detergent, enzymes, and solvent to remove cells from tissue. This MATRACELL™ technology also effectively removes donor DNA from the ADM ensuring a biocompatible scaffold to facilitate repair. All these screenings, tests, and treatments are designed to eliminate the risk of disease transmission. The remaining intact acellular framework contains native growth factors, proteoglycans, hyaluronic acid, collagen, fibronectin, and elastin, therefore promoting wound healing.

A-FLEX is terminally sterilized with low dose gamma irradiation to provide a medical-device grade Sterility Assurance Level (SAL) of 10^{-6} .

Labeling

Since this will be an open-label study, study product will be identified. The Instructions for Use for A-FLEX will be provided in the site study binders.

Storage and Handling of Investigational Product

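### The primary analysis runs on both the intent-to-treat and per-protocol sets at 0.05 with no rule for which decides, and the per-protocol set drops patients who have a valid 1-year MRI

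*Combined protocol and SAP*

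**What the plan says.** Section 5 (Sample Size Justification and Statistical Analysis) puts the primary analysis on two populations: "The primary analysis will be conducted on both the intent to treat and the per protocol populations". The decision rule is a single sentence: "Primary analysis results will be declared statistically significant if the two-sided p-value is less than 0.05". The section gives no order between the sets, no split of the 0.05, no requirement that both succeed and no plan for discordant results. Only the covariate-adjusted analyses are labelled secondary, so per-protocol is not supportive by default.

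The sets are defined as follows.

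- Intent to treat: "The intent to treat population will be comprised of all subjects that have completed rotator cuff repair surgery". This is not everyone randomised.
- Per protocol: "The per protocol population will be comprised of all subjects that have completed all study visits and did not have any major protocol violations", with the examples "e.g., missed visits, noncompliance with postsurgical instructions, etc".

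Section 3C schedules "serial US exams at 6 weeks, 3 months, 6 months, 9 months and 1 year postop, and MRI exam at 1 year postop". That is five post-operative visits, of which the main outcome, MRI healing, uses only the last. Section 6 (Labeling) adds: "Since this will be an open-label study, study product will be identified".

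**The concern.** The question is one of superiority: section 5 expects re-tear of about 40% in controls and about 20% with the graft. When two analyses of one question are both called primary, the plan has to say what counts as success. Without that, the sponsor could report whichever set favours the graft, or could be left with one significant and one non-significant primary result and no defined answer.

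The second issue is who is in the per-protocol set. A patient who missed the 9-month visit but had the 1-year MRI has a complete outcome and is still removed. Attendance and compliance after surgery come after randomisation. In an open-label trial they may be influenced by the arm and by how the shoulder is doing. Section 5 itself expects fewer controls to complete, partly because of tear severity, and the summary of changes attributes the increase to 70 patients to large drop-out. A comparison within such a set is not protected by randomisation.

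**Working it through.** **Inputs from the documents.** 35 patients per arm (Synopsis; section 1). Re-tear about 40% and 20%, two-sided 0.05 (section 5). Five post-operative visits (section 3C).

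**Assumptions.** The documents give no per-protocol retention, so the share kept, f, is varied from 0.9 to 0.6, with exclusion at random. No test is named for the primary comparison, so an uncorrected pooled z-test and Fisher's exact test are both tried.

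**1. The stated 0.05 for a single analysis.** The z-test is z = (p1 − p2) / √[p(1 − p)(1/n1 + 1/n2)]. With a 40% re-tear rate in both arms and 35 per arm, one intent-to-treat analysis is falsely significant in 4.8% of 400,000 simulated trials. With Fisher's test, one analysis has a type I error of about 2.8%.

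**2. Two nested analyses.** The per-protocol set lies inside the intent-to-treat set, so under random exclusion the two z statistics correlate at √f. The chance that at least one is significant is 1 − P(|Z1| ≤ 1.96 and |Z2| ≤ 1.96). For f = 0.9, 0.8, 0.7 and 0.6 this gives 6.5, 7.1, 7.6 and 8.0%. The value for independent tests, 1 − 0.95² = 9.75%, does not apply. Simulated z-test results:

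| Share kept | Either significant, no true difference | Both significant, no true difference | Verdicts disagree, 40% vs 20% |
|---|---|---|---|
| 90% | 6.5% | 3.5% | 10.6% |
| 80% | 7.1% | 2.9% | 15.8% |
| 70% | 7.7% | 2.5% | 20.4% |
| 60% | 8.1% | 2.0% | 24.5% |

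With Fisher's test the either-significant rate is about 4-5% over the same range, up from about 2.8% for one analysis.

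**3. What disagreement consists of.** At 40% vs 20% and f = 0.8, intent to treat is significant in 45.4% of trials, per protocol in 37.7% and both in 33.6%. Intent to treat alone: 45.4 − 33.6 = 11.8%. Per protocol alone: 37.7 − 33.6 = 4.1%. Most disagreement comes from the smaller per-protocol sample.

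**4. How many might be excluded.** If each of five visits is attended with probability 0.90 or 0.95, independently (an assumption), all five are attended by 0.90⁵ = 59% or 0.95⁵ = 77%. Positive correlation between visits would raise these shares.

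**5. Selective exclusion (assumed, 40% re-tear in both arms, z-test).** Suppose 80% of patients are kept, except graft-arm re-tears, kept at 60%. The expected graft re-tear rate in the per-protocol set is 0.4 × 0.6 / (0.4 × 0.6 + 0.6 × 0.8) = 0.24 / 0.72 = 33%, against 40% in controls. Per-protocol type I error is then 8.0%, and the either-set rate about 10.3%. If re-tears are kept at 60% in both arms, both rates are 33% and per-protocol type I error is 5.2%. In these scenarios the false difference appears when exclusion differs by arm.

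**The case against.** A reader might infer that the plan gives two chances to win and therefore exceeds 0.05. The documents do not support that as a fact. Section 5 never says that either set may carry the claim alone, and requiring both is an equally open reading, under which the error is about 2-3.5%. Even with an either-set rule, Fisher's exact test keeps the error at about 4-5%. The excess needs both a permissive rule and a less conservative test, and the plan states neither. This objection stands as to size. It does not remove the defect, which is that the rule is missing.

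A reader might also infer that the per-protocol set is outcome-dependent. The documents make that plausible but do not show it, and exclusion tied to outcome equally in both arms leaves the error near 5%. Nor are conflicting verdicts likely: at 11-24%, agreement is the more common result, and a per-protocol-only success occurs in only about 3.5-4.4% of trials at 40% vs 20%. Finally, the text speaks of completed visits. It does not say that an unfilled questionnaire at an attended visit excludes a patient.

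On the remedy, analysing everyone randomised is more than a wording change. Section 5 says controls withdrawn for augmentation may be followed for safety, so their 1-year MRI is not assured. Section 2D analyses patients whose repair could not be done as a separate group. That objection stands, and the fix has to deal with both groups.

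**Conclusion.** The concern holds in this form. The plan names two primary analysis sets at two-sided 0.05 without saying which decides, and nothing elsewhere in the document settles it. The type I error is therefore undefined: over the range examined it runs from about 2% (both sets required, z-test) to about 8.1% (either set, z-test), with random exclusion and 60-90% retention. At the planned effect, the two z-test verdicts would differ in roughly one trial in nine to one in four.

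Separately, the per-protocol definition discards complete 1-year MRI outcomes because of events after randomisation. Bias from this is plausible in an open-label trial that expects unequal completion, but the documents give neither its direction nor its size, and the selective-exclusion figures are illustrations only. This should be corrected before the analysis.

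**What to change.** - Name one primary result in section 5: MRI healing at 1 year, all randomised patients in their assigned arm, two-sided 0.05. Say explicitly that this replaces the current intent-to-treat set of surgery completers.
- State that controls who receive augmentation are analysed as randomised and are asked to have the 1-year MRI already in the schedule. Reconcile this with the section 5 sentence on withdrawn controls.
- State how patients with no repair (the separately analysed group in section 2D) and patients with a missing 1-year MRI are counted in the primary result, with a sensitivity analysis for that choice.
- Make per-protocol supportive only. Do not exclude a patient who has a 1-year MRI for missing an interim visit.

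**Cost.** Most of this is wording and needs no additional patients or new procedures. The sponsor gives up a possible second route to significance, and patients withdrawn from the control arm must be kept in follow-up to the 1-year MRI, which takes some site effort.
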